11.6.4. Duration of Response

Duration of response will be calculated for all responders from the date of the earliest assessment of CR or PR to the date of relapse or death, whichever occurs earlier, or the last disease assessment date for subjects without a relapse or death. Duration of SD will be calculated for subjects whose best response is CR, PR, or SD from the day study drug was first taken to the date of disease progression or death, whichever occurs earlier, or the last disease assessment for subjects without disease progression or death.

Duration of response and duration of SD will be summarized with descriptive statistics including arithmetic mean, standard deviation, median, and range will be summarized for subjects who have overall responses.

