## 1.0 INTRODUCTION

The purpose of this document is to provide details of the planned analyses for the Phase 1 and 2 ASTX029-01 study. The study is to assess the safety, PK, pharmacodynamics, and preliminary clinical activity of ASTX029 administered orally to subjects ≥18 years of age with advanced solid malignancies who are not candidates for approved or available therapies.

The primary objectives of the Phase 1 portion of this study are to assess safety and to identify the MTD, the RP2D, and the recommended dosing regimen of ASTX029 administered orally. The primary objective of the Phase 2 portion of this study is to assess preliminary clinical activity, as determined by objective response rate (ORR) in tumors characterized by gene aberrations in the MAPK signal pathway that may confer sensitivity to ASTX029.

The analyses specified in this document supersede the high-level analysis plan described in the protocol. Analyses and statistical reporting for ASTX029-01 subjects, with the exception of the analyses that are described in a separate Pharmacometrics Analysis Plan (PAP), will be conducted by Taiho Oncology Biostatistics department using SAS version 9.4 or higher.

This Statistical Analysis Plan (SAP) is based on the ASTX029-01 protocol amendment 5.0 (dated 14 April 2022).

Specifications for data tables, listings and figures are detailed in a separate document.

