### 7.5.2 Duration of Response

Duration of response will be calculated for all responders from the date of the first documentation of CR or PR to the date of progress or death, whichever occurs first. Duration of SD will be calculated for subjects whose best response is CR, PR, or SD from the day study drug was first taken to the date of disease progression or death, whichever occurs earlier, or the last disease assessment for subjects without disease progression or death.

Duration of response and duration of SD will not be estimated for subjects who leave the study prior to a first assessment of response nor for subjects whose best response is progressive disease.

Duration of response and duration of SD will be analyzed using a K-M method, with the duration being censored at the time of the date of study termination for subjects without a relapse or disease progression. Duration of response and duration of SD will be summarized.

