#### 7.5.3 Survival

The OS is defined as the number of days from the day study drug was first taken to the date of death (regardless of cause). Subjects without a documented death date will be censored on the last date they were known to be alive. The OS will be presented using a Kaplan Meier estimate. The 95% CI for median OS will be provided using the Kaplan-Meier method with the log-log transformation. All subjects in the Efficacy Analysis Set (Section 5.3) will be included in the OS analysis. The OS rate at 3, 6, 9 and 12 months (and in subsequent 6-month increments if there are participants still at risk) will be estimated with corresponding two-sided 95% CIs.

Frequency (number and percentage) of participants with death events and censoring reasons will be presented with the overall event and censor rates. The event and censoring reasons are as follows:

- Death
- Ongoing and no death
- Withdrawal of consent
- Lost to follow-up.

The OS time or censoring time and the reasons for censoring will also be presented in a listing

The PFS is defined as the number of days from the start of the study drug to disease progression or death, whichever occurs first. The PFS will be analyzed using a Kaplan-Meier method, with PFS time being censored on the date of the last disease assessment. The 95% CI for median PFS will be provided using the Kaplan-Meier method with the log-log transformation. All subjects in the Efficacy Analysis Set (Section 5.3) will be included in the PFS analysis.

Progression of disease (PD) is included as an overall response in Table 1 above, and combines evaluation target, non-target, and new lesions. Target lesion response of PD is at least a 20% increase in the sum of diameters of target lesions, taking as reference the smallest sum on study (this includes the baseline sum if that is the smallest on study). Non-target lesion response of PD is unequivocal progression of existing nontarget lesions. The appearance of 1 or more new lesions is also considered progression of disease. Additional details can be found in Appendix 3 of the protocol, which is based on RECIST v1.1 (Eisenhauer et al 2009).

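### SAP 7.5.2 treats death as an event when it defines duration of response and duration of SD, but as a censoring in its Kaplan-Meier sentence; programmed as written, that sentence biases both durations upward

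*SAP*

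**What the plan says.** The first paragraph of SAP 7.5.2 defines the two durations. DOR runs "from the date of the first documentation of CR or PR to the date of progress or death, whichever occurs first". Duration of SD, which covers subjects whose best response is CR, PR or SD, runs from first dose "to the date of disease progression or death, whichever occurs earlier, or the last disease assessment for subjects without disease progression or death". Death ends both. For duration of SD the paragraph also says who is event-free: only subjects with neither progression nor death.

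The last paragraph of the same section moves both durations to a Kaplan-Meier analysis, "with the duration being censored at the time of the date of study termination for subjects without a relapse or disease progression". This names progression but not death, and it uses a different censoring date.

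Three other places bear on the point:

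- Protocol 11.6.4 ends DOR in line with the SAP definitions: "to the date of relapse or death, whichever occurs earlier, or the last disease assessment date for subjects without a relapse or death". It plans no Kaplan-Meier analysis: "Duration of response and duration of SD will be summarized with descriptive statistics including arithmetic mean, standard deviation, median, and range".
- SAP 7.5.3 counts death as an event for PFS: "The PFS is defined as the number of days from the start of the study drug to disease progression or death, whichever occurs first". It censors PFS at the last disease assessment.
- SAP 1.0 states: "The analyses specified in this document supersede the high-level analysis plan described in the protocol". SAP 7.9, which lists changes from the protocol, does not mention either duration.

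**The concern.** Someone coding the event indicator has two instructions that disagree for one group: responders, or subjects with stable disease, who die before progression is documented. Such deaths are plausible here. After cycle 4, scans are due every 4 cycles of 21 days (give or take a cycle), nominally 12 weeks apart. Protocol Appendix 3 also says that symptomatic deterioration is not an objective response category, so a subject can decline and die without RECIST progression.

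Censoring these deaths is informative censoring: it takes bad outcomes out of the event count. DOR is a secondary endpoint of a trial without a control arm and is read alongside the ORR, so an upward bias would favour the drug. It would also make the report inconsistent. Duration of SD has the same start and the same end events as PFS, so one death could be an event in the PFS table and a censoring in the duration-of-SD table.

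**Working it through.** **Plan's own figure.** Neither document states a number for DOR or duration of SD, so there is nothing to reproduce for the claim itself. The design figure that sets responder numbers does reproduce. For 10 + 19 subjects, continuing with at least 2 responses and rejecting with at least 6, the rejection probability is the sum over x = 2 to 10 of P(Bin(10, p) = x) × P(Bin(19, p) ≥ 6 − x). This gives 0.047 at p = 0.1 and 0.805 at p = 0.3, in line with the stated 0.05 and 80%. It uses responses only, so the duration wording does not touch it.

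**One subject under both rules.** Scans fall at weeks 6, 12 and 24 (ends of cycles 2, 4 and 8). Suppose PR at week 6, no progression at weeks 12 and 24, and death at week 30.

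- Definition paragraph: DOR event at 30 − 6 = 24 weeks.
- Kaplan-Meier sentence: no relapse or progression, so censored. The time is 24 weeks if study termination means the subject's own exit (SAP 7.1 lists death as a reason for leaving the study), and longer if it means a study-level date.

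**Direction.** The Kaplan-Meier curve is a product of factors 1 − d/n. Recoding a death as censored on the same day replaces its factor by a larger one (1 if it was the only event then) and leaves later risk sets unchanged. Moving the censoring later also enlarges later risk sets. The curve therefore stays equal or rises.

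**Six responders**, the smallest number that rejects the null (invented times): progression at months 2, 4, 8 and 10; death without progression at months 3 and 6; study termination at month 14. The median is the first time the curve is at or below 0.5.

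| Treatment of the two deaths | Curve at 4 | Curve at 8 | Median |
|---|---|---|---|
| Event | 5/6 × 4/5 × 3/4 = 0.50 | 0.50 × 2/3 × 1/2 = 0.17 | 4 months |
| Censored at death | 5/6 × 3/4 = 0.63 | 0.625 × 1/2 = 0.31 | 8 months |
| Censored at month 14 | 5/6 × 4/5 = 0.67 | 0.667 × 3/4 = 0.50 | 8 months |

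**Large sample.** Assumptions, none of them in the documents: constant hazards, true median 6.0 months, and a share f of first events that are deaths without progression. The total hazard is λ = ln 2 / 6 per month and the progression hazard is (1 − f)λ. With deaths censored at the date of death, the median is ln 2 / [(1 − f)λ] = 6/(1 − f). For deaths censored at study termination, a simulation of 200,000 subjects took termination as uniform over 6 to 30 months after response.

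| f | Censored at death: 6/(1 − f) | Censored at study termination (simulated) |
|---|---|---|
| 5% | 6.3 months (+5%) | 6.5 months (+8%) |
| 10% | 6.7 months (+11%) | 7.0 months (+17%) |
| 20% | 7.5 months (+25%) | 8.5 months (+42%) |
| 30% | 8.6 months (+43%) | 10.8 months (+81%) |

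The same simulation gave 6.3, 6.7, 7.5 and 8.6 months for censoring at death, which agrees with the closed form.

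**The case against.** The best defence is that the definitions fix the event, and that the Kaplan-Meier sentence only supplies a date for subjects still event-free, naming progression as loose shorthand. The PFS text in SAP 7.5.3 is built that way: the definition names death, and the censoring clause gives only a date. A programmer who reads 7.5.2 like this keeps deaths as events, and no bias arises. This stands as a reason for conditional wording: a reader might infer that the reported durations will be overstated, but the documents do not establish that. It does not remove the conflict. Unlike the PFS clause, the sentence in 7.5.2 does say who is censored, and its description fits a subject who died without progression.

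A reader might also infer that this sentence alone decides event status for both durations. That is not so for duration of SD, where the definition already limits the event-free group to subjects with neither progression nor death. For SD the section therefore contains a correct rule and a conflicting one. Only for DOR is the Kaplan-Meier sentence the sole censoring clause in the SAP.

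Finally, the consequence is limited. DOR is secondary, duration of SD is not a listed endpoint, efficacy is summarised descriptively, and no duration threshold drives a decision. With about six responders, a median is imprecise under either rule. All of that stands, and it bounds the importance of the point.

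**Conclusion.** The point holds as an internal contradiction in SAP 7.5.2. Nothing else in the SAP resolves it, and Protocol 11.6.4 cannot be relied on to do so because the SAP says it takes precedence. An upward bias follows on two conditions: the Kaplan-Meier sentence is programmed as written, and at least one responder or SD subject dies without documented progression. The direction is then certain; the size is not known.

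The medians of 6.7, 7.5 and 8.6 months are illustrations that rest on constant hazards, an assumed 6.0-month median, assumed shares of 10%, 20% and 30%, and censoring at the date of death. They should not be read as estimates for this trial, since the documents supply none of these inputs and the sentence itself names study termination. Under that wording, with a termination date later than the death, the inflation would be greater. Nor do the documents support reading the omission as a deliberate change of endpoint: both the definitions and the PFS rule keep death as an event, which points to a drafting slip. The ORR decision rule does not change. The correction should be made, but it does not bear on the primary analysis.

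**What to change.** Rewrite the Kaplan-Meier sentence in SAP 7.5.2 to say that, for both DOR and duration of SD, the event is progression or death, whichever comes first; that a death without documented progression is an event on the date of death; and that a subject is censored only if neither has happened.

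In the same edit, reconcile the censoring date. Study termination conflicts with the last disease assessment used in the definition of duration of SD, in the PFS rule of SAP 7.5.3 and in Protocol 11.6.4. It also credits time in which nobody assessed the disease and, if read as a study-level date for a subject who died, time after death.

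The cost is one sentence and no new data. Reported durations may come out shorter than under the literal wording. Because the trial is open-label, the choice should be fixed in writing before the duration analyses are run.

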#### 7.5.3 Survival

The OS is defined as the number of days from the day study drug was first taken to the date of death (regardless of cause). Subjects without a documented death date will be censored on the last date they were known to be alive. The OS will be presented using a Kaplan Meier estimate. The 95% CI for median OS will be provided using the Kaplan-Meier method with the log-log transformation. All subjects in the Efficacy Analysis Set (Section 5.3) will be included in the OS analysis. The OS rate at 3, 6, 9 and 12 months (and in subsequent 6-month increments if there are participants still at risk) will be estimated with corresponding two-sided 95% CIs.

Frequency (number and percentage) of participants with death events and censoring reasons will be presented with the overall event and censor rates. The event and censoring reasons are as follows:

- Death
- Ongoing and no death
- Withdrawal of consent
- Lost to follow-up.

The OS time or censoring time and the reasons for censoring will also be presented in a listing

The PFS is defined as the number of days from the start of the study drug to disease progression or death, whichever occurs first. The PFS will be analyzed using a Kaplan-Meier method, with PFS time being censored on the date of the last disease assessment. The 95% CI for median PFS will be provided using the Kaplan-Meier method with the log-log transformation. All subjects in the Efficacy Analysis Set (Section 5.3) will be included in the PFS analysis.

Progression of disease (PD) is included as an overall response in Table 1 above, and combines evaluation target, non-target, and new lesions. Target lesion response of PD is at least a 20% increase in the sum of diameters of target lesions, taking as reference the smallest sum on study (this includes the baseline sum if that is the smallest on study). Non-target lesion response of PD is unequivocal progression of existing nontarget lesions. The appearance of 1 or more new lesions is also considered progression of disease. Additional details can be found in Appendix 3 of the protocol, which is based on RECIST v1.1 (Eisenhauer et al 2009).

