The ORR, PFS, and DOR endpoints will be based on the investigator's assessment of target and non-target lesions according to RECIST v1.1; computed tomography (CT) or magnetic resonance imaging (MRI) scans (or other appropriate disease evaluation method, including tumor marker measurement, as applicable) will be performed at baseline and every 2 cycles for the first 4 cycles, and then every 4 cycles (± 1 cycle) thereafter until clinical and/or radiographic disease progression, death, or the subject withdraws consent. Subjects will be followed for OS.

Pharmacokinetics Assessments:

Serial blood sampling (up to 24 hours postdose) on the following study days will allow assessment of systemic exposures of ASTX029:

- Phase 1: Cycle 1 Day 1 (C1D1), Cycle 1 Day 2 (C1D2), Cycle 2 Day 1 (C2D1), and Cycle 2 Day 2 (C2D2) for Regimen 1 and C1D1, C1D2, Cycle 1 Day 14 (C1D14), and Cycle 1 Day 15 (C1D15) for Regimen 2.
- Phase 2: C1D1, C1D2, C2D1, and Cycle 3 Day 1 (C3D1) for Regimen 1 and C1D1, C1D2, C1D14, C1D15, and C3D1 for Regimen 2.

At specified study visits, blood samples, including predose and trough samples, will be collected. Additional ad hoc blood sample(s) may be collected per investigator discretion, for PK measurement at any time, including after the last dose, if there is a suspected safety issue. Plasma drug concentration data will be used to determine the PK parameters listed under Secondary Endpoints in all subjects during Cycle 1 and Cycle 2 if data are evaluable.

Pharmacodynamic and Biomarker Assessments:

The pharmacodynamic modulation and target engagement will be explored in fresh tumor tissue biopsies (when available). Identification and monitoring of potential biomarkers (DNA, RNA, and protein) of ASTX029 activity will be assessed in ctDNA, blood, and tumor tissue biopsies.

Safety Assessments:

At each study visit, safety will be monitored by recording AEs, serious adverse events (SAEs), DLTs, and concomitant medications; additional safety assessments at selected visits include complete or symptom-directed physical examinations (PEs), weight and height, vital signs, Eastern Cooperative Oncology Group (ECOG) performance status, 12-lead ECGs, ECHO/MUGA scans, and clinical laboratory tests (hematology, coagulation, serum chemistry, and urinalysis). All AEs will be graded by National Cancer Institute (NCI) Common Terminology Criteria for Adverse Events (CTCAE) v4.03.

Sample Size and Statistical Analyses: Sample Size Calculation:

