9. STUDY ASSESSMENTS AND PROCEDURES

9.1. Preliminary Clinical Activity Assessments

Measurable disease according to RECIST v1.1 (Appendix 3) will be assessed using CT or MRI scans at baseline (screening), every 2 cycles (\pm 7 days) for the first 4 cycles, and then every 4 cycles (\pm 1 cycle) thereafter until clinical and/or radiographic disease progression, death, or the subject withdraws consent. Tumor markers (if applicable) should be measured at the same time points as the time points for radiological assessments.

For subjects whose disease is not measurable using RECIST v1.1, disease status must be reliably and consistently followed using another generally acceptable method.

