9.4.13. Treatment Termination Visit

This visit should occur within 7 days after the last study treatment or within 3 days before starting new cancer treatment and before the 30-day Safety Follow-up visit. (Note: hematology, serum chemistry, coagulation, urinalysis, and pregnancy tests may be performed on the day before the visit if more convenient.) If a subject discontinues study treatment at a scheduled visit, the assessments at that visit can be used to fulfill the Tx Term visit requirements.

The visit should occur when a subject permanently discontinues study treatment, regardless of whether or not the subject plans to continue participating in the study, for long term follow up of health status (unless consent to continue study participation is withdrawn by the subject).

- Perform symptom-directed PE (Section 9.4.1).
- Record vital signs (Section 9.4.2).
- Evaluate ECOG performance status (Appendix 1).
- Perform 12-lead ECG in triplicate (Section 9.4.4).
- Perform ECHO or MUGA scan.
- Record AEs and concomitant medications.
- Collect blood samples for hematology, coagulation, and serum chemistry laboratory tests; collect urine sample for urinalysis (Table 10).
- Perform serum or urine pregnancy test for women of child-bearing potential only.
- Collect blood sample for ctDNA (Section 9.2.2, Table 8).
- Review dosing diary to assess dosing compliance.
- If the last disease assessment was >12 weeks prior to study treatment withdrawal and disease progression had not been documented, assess subject's disease by CT or MRI

scan (or other appropriate disease evaluation method, including tumor marker measurement, as applicable).

9.4.14. **30-day Safety Follow-up Visit**

This visit must occur 30 (\pm 5) days after the last dose of study treatment or within 3 days before starting a new cancer treatment.

- Perform symptom-directed PE (Section 9.4.1).
- Record vital signs (Section 9.4.2).
- Evaluate ECOG performance status (Appendix 1).
- Record AEs and concomitant medications.

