Best response determination in studies where confirmation of CR or PR is not required: Best response in these studies is defined as the best response across all time points (eg, if a subject has SD at first assessment, PR at second assessment, and PD on last assessment, he or she will have a best overall response of PR). When SD is believed to be best response, it must also meet the protocol-specified minimum time from baseline (6 weeks). If the minimum time is not met when SD is otherwise the best time point response, the subject's best response depends on the subsequent assessments. For example, if a subject has SD at first assessment, but PD at the second assessment, and does not the meet minimum duration for SD, he or she will have a best response of PD. The same subject lost to follow-up after the first SD assessment would be considered inevaluable.

Special Notes on Response Assessment

When nodal disease is included in the sum of target lesions and the nodes decrease to 'normal' size (<10 mm), they may still have a measurement reported on scans. This measurement should

be recorded even though the nodes are normal, in order not to overstate progression should it be based on increase in size of the nodes. As noted earlier, this means that subjects with CR may not have a total sum of 'zero' on the eCRF.

Subjects with a global deterioration of health status requiring discontinuation of treatment without objective evidence of disease progression at that time should be reported as 'symptomatic deterioration.' Every effort should be made to document objective progression even after discontinuation of treatment. Symptomatic deterioration is not a descriptor of an objective response: it is a reason for stopping study therapy. The objective response status of such subjects is to be determined by evaluation of target and nontarget disease.

For equivocal findings of progression (eg, very small and uncertain new lesions; cystic changes or necrosis in existing lesions), treatment may continue until the next scheduled assessment. If at the next scheduled assessment, progression is confirmed, the date of progression should be the earlier date when progression was suspected.

Frequency of Tumor Re-evaluation

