In this study, tumor measurement will be conducted at the end of every 2 cycles (\pm 7 days) for the first 4 cycles and then every 4 cycles (\pm 1 cycle) thereafter until clinical and/or radiographic disease progression, or death, or the subject withdraws consent. Scan dates should not be adjusted or rescheduled due to dose interruption of any type.

Baseline tumor assessments must be performed within 3 weeks (21 days) prior to the first dose of treatment.

All efforts should be made to ensure consistency between the baseline measurements and all subsequent measurements in reference to utilization of scanning method, equipment, technique (including slice thickness and field of view), and radiographic interpreter.

The radiographic evaluation must include CT or MRI scanning of the known sites of involvement, as well as the chest, abdomen, and pelvis if they are not the primary target. Any additional suspected sites of disease should also be imaged. All evaluations should meet the standard of care for imaging of lesions in the respective organ(s) and should conform to the image acquisition guidelines according to institutional standards.

All target and nontarget sites are evaluated at each time point of tumor assessment.

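### Scheduled scans end at clinical progression but PFS is read from RECIST lesion criteria, so clinical progressors with no later objective PD are censored early or counted only at death

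*SAP*

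**What the plan says.** SAP 7.5.3 gives the definition: "The PFS is defined as the number of days from the start of the study drug to disease progression or death, whichever occurs first". It then explains progression: "Progression of disease (PD) is included as an overall response in Table 1 above, and combines evaluation target, non-target, and new lesions". The rest of that paragraph lists the target, non-target and new-lesion criteria and points to Protocol Appendix 3. Clinical progression is not mentioned. The Protocol Synopsis (efficacy assessments) has the same basis: "The ORR, PFS, and DOR endpoints will be based on the investigator's assessment of target and non-target lesions according to RECIST v1.1". The analysis is Kaplan-Meier, "with PFS time being censored on the date of the last disease assessment"; Protocol 11.6.2 has the same rule.

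The imaging schedule has a wider stopping point. In Protocol 9.1 scans continue "thereafter until clinical and/or radiographic disease progression, death, or the subject withdraws consent", and Appendix 3 repeats it: "thereafter until clinical and/or radiographic disease progression, or death, or the subject withdraws consent". Table 11 footnote w and Table 12 footnote v agree. At the Treatment Termination visit (Protocol 9.4.13) a scan is required only on this condition: "If the last disease assessment was >12 weeks prior to study treatment withdrawal and disease progression had not been documented".

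Appendix 3 also pulls the other way. It classes symptomatic deterioration as a reason for stopping therapy and not as an objective response category, but adds: "Every effort should be made to document objective progression even after discontinuation of treatment". Protocol 9.4.15 collects a progression date by telephone every 3 months for subjects who had not progressed when they stopped treatment.

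**The concern.** The event definition and the scan schedule do not match. A subject whose disease worsens clinically leaves the scan schedule at the point where a RECIST PD date would have to be obtained. If none is obtained later, the censoring rule goes back to a scan on which the disease had not yet progressed, or the event waits until death. Either way the subject's progression is missing from the curve when it happens, and the reason is the progression itself. Kaplan-Meier assumes that censored subjects have the same prospects as those still at risk. These subjects have worse prospects, so the curve is biased upward. At stake is how far the PFS and DOR figures can be trusted as descriptions of activity in each cohort.

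**Working it through.** **1. Does the termination scan close the gap?** Cycles are 21 days. For the first 4 cycles scans fall every 2 × 21 = 42 days (6 weeks), so the gap to the last on-schedule scan is well under 12 weeks and the condition is not met. After that, scans fall every 4 × 21 = 84 days (12 weeks), with a window of one cycle, so 84 + 21 = 105 days (15 weeks) at the late end. The condition of more than 12 weeks is then met only when a scan has run past its nominal date or been missed. The termination scan seldom helps.

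**2. Do other passages close it?**
- Protocol 5.4.1 encourages assessment according to the protocol after discontinuation, and asks for activity evaluations at the termination visit where possible. But the protocol's own schedule ends at clinical progression, and its termination scan is conditional.
- Protocol 5.4.2 asks for every effort on progression data after withdrawal, but exempts subjects who withdrew because of progression.
- Protocol 9.4.15 collects a later date only from subjects without progression at discontinuation. A subject who stopped for clinical progression is arguably outside that wording, and the SAP does not say whether such a date counts as an event.
- Appendix 3 asks for objective progression to be documented. Where that succeeds, the subject is counted at the later PD scan.

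The affected group is therefore clinical progressors without later objective documentation. A subject who stops before any post-baseline scan is also in the PFS set, and the SAP gives no censoring date for that case.

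**3. Size.** The documents state no PFS median, rate or event count, so there is nothing to reproduce. All inputs below except the scan times are assumptions:
- share of subjects with clinical-only progression and no later PD scan: 5%, 10%, 20%, 30%;
- median time to progression: 2 or 4 months;
- median survival after progression: 3 or 6 months;
- exponential times, rate = ln 2 / median;
- scans at days 42 and 84, then every 84 days;
- data cut 12 to 24 months after entry; 200,000 simulated subjects per scenario.

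The Kaplan-Meier estimate is S(t) = Π(1 − d/n), with d events and n at risk at each event time. 6-month PFS is S(182.6 days). Three treatments of clinical progressors are compared: (A) event on the clinical progression date; (B) event at death, or censored at the last scan before progression if alive at the cut; (C) always censored at that last scan. Entries are 6-month PFS in percent, as A → B / C.

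| Share | Progression 2 mo, survival 3 mo | 2 mo, 6 mo | 4 mo, 3 mo | 4 mo, 6 mo |
|---|---|---|---|---|
| 5% | 14.5 → 16.2 / 15.7 | 14.6 → 16.9 / 15.8 | 38.0 → 39.5 / 39.7 | 38.1 → 39.9 / 39.8 |
| 10% | 14.4 → 18.0 / 16.9 | 14.5 → 19.1 / 16.9 | 37.9 → 40.9 / 41.4 | 38.0 → 42.0 / 41.6 |
| 20% | 14.3 → 21.5 / 19.7 | 14.3 → 23.7 / 19.8 | 37.6 → 43.6 / 45.1 | 37.8 → 45.6 / 45.3 |
| 30% | 14.0 → 24.7 / 22.9 | 14.0 → 28.3 / 23.0 | 37.5 → 46.4 / 49.3 | 37.4 → 49.2 / 49.2 |

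The smallest gap is 15.7 − 14.5 = 1.2 points and the largest 28.3 − 14.0 = 14.3 points. By share the gaps are 1.2 to 2.3 (5%), 2.4 to 4.6 (10%), 5.4 to 9.4 (20%) and 8.9 to 14.3 (30%). All 16 scenarios go upward under both B and C.

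**4. The median.** The SAP names the median for PFS; landmark rates are planned only for OS. The curve falls mainly at scan dates, so the median moves only if the 50% crossing shifts to another step. It stayed at 84 / 30.4375 = 2.76 months or 168 / 30.4375 = 5.52 months in every scenario except a 30% share with 2-month progression under B, where it went from 2.76 to 3.13 or 3.83 months. Other assumptions can move it more. With a 14-week true median, a 20% share and 13-week survival after progression, the median goes from 18.8 to 24.0 weeks and 24-week PFS from 30.2% to 36.5%. At the same share and survival, true medians of 8, 17.4 or 20 weeks give no shift, and those between 10 and 15 weeks give about 2 to 8 weeks.

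**5. DOR.** SAP 7.5.2 censors by Kaplan-Meier at study termination for subjects without relapse or progression, whereas Protocol 11.6.4 uses the last disease assessment. Under the SAP rule a responder with clinical progression only can accrue response time beyond the last scan. No DOR figure was computed.

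**The case against.** The strongest reply is that the plan follows a recognised convention. Appendix 3 keeps symptomatic deterioration out of objective response, and counting investigator-judged clinical progression as an event in an open-label study brings its own subjectivity. This stands: it is a good reason to keep RECIST-only PFS as the main estimate and to use clinical progression only in a sensitivity analysis. It does not answer the informative censoring.

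It can also be said that the SAP never states that only RECIST PD counts. That is correct. The reading rests on its PD paragraph together with the Synopsis sentence, and Table 1 is written for subjects with measurable disease at baseline. But no other route for clinical progression is given.

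Several stronger readings are tempting and are not supported:
- That clinical progressors usually never receive a RECIST PD date. Protocol 5.4.1, 9.4.15 and Appendix 3 all provide for later information, and the frequency is unknown.
- That SAP 5.3 contradicts SAP 7.5.3 because it keeps early clinical progressors in the ORR and DCR denominator. That is an evaluability rule; subjects who stop for toxicity are kept in the same way, and it does not declare anyone progressed.
- That PFS will be judged against a historical value. The only benchmark stated is the ORR null of 0.1.
- That DOR suffers the same censoring at the last scan. SAP 7.5.2 uses study termination.

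**Conclusion.** The point holds for clinical progressors without later objective PD. Applied as written, the plan censors them before their deterioration or counts them only at death, and the Kaplan-Meier PFS curve is biased upward. The direction is firm; the size is not. Under assumed shares of 5% to 30%, 6-month PFS rises by about 1 to 14 points, and the planned median often does not move. These figures rest wholly on the assumed share, the exponential times, and no later scan in the affected subjects. A reader might infer a demonstrated overstatement of a given size, but the documents supply no input from which to establish one. PFS is a secondary endpoint summarised descriptively with no hypothesis attached, so ORR and the Simon two-stage decisions are untouched. The change is worth making, but does not threaten the primary conclusion.

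**What to change.** Keep RECIST-only PFS as the main estimate. In SAP 7.5.2 and 7.5.3:
- add a sensitivity Kaplan-Meier estimate that counts treatment discontinuation for clinical progression without RECIST PD as an event on that date;
- list the number of such subjects per cohort;
- state whether a progression date from the Protocol 9.4.15 follow-up counts as an event.

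Protocol 5.4.1 already requires the discontinuation reason on the eCRF. The form itself is not in the documents, so the sponsor should check that it separates clinical from radiographic progression. If it does not, a progression reason with no RECIST PD on record would identify the group.

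The scan-stopping text in Protocol 9.1, Table 11 footnote w, Table 12 footnote v and Appendix 3 must be reconciled with the Appendix 3 instruction to document objective progression after discontinuation.

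The cost is some wording and one extra analysis, with a somewhat less favourable and more investigator-dependent PFS figure shown beside the main one.
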